1.1.1 Sample size

No formal statistical hypotheses are being tested and no formal sample size calculation has been performed. The aim of the registry is to collect additional data on treatment effects of a specific indication for which Varithena® is approved but has not been examined in detail. Previous feasibility metrics indicate approximately 200 patients can be enrolled within one year.

1.1.2 Data collection schedule and assessments

Registry Visit	Screening/ Baseline	Enrollment/ Treatment ^a (Day 0)	Week 1 Follow-Up Visit ^b	Week 2 through Wound Closure (at WCC) Weekly	Week 12 (±1wk) Follow-Up Visit	3 Months (±1wk) Post-Closure (phone call)	6 Month (±1wk) Follow-Up (phone call)	Month 12 (±1wk) Follow-Up Visit
Informed consent	X							
Duplex ultrasound of superficial and deep veins	X		X (as necessary)					
Screening: eligibility criteria	X							
Demographics, comorbidities, wound history	X							
Wound Characteristics			X ^c					
Varithena [®] treatment		X (as necessary) ^d		X (as necessary) ^d				
Hospitalizations for wound?	X		X		X	X	X	X
Patient training to use sDCT			X					
Review of VLU recurrence (if applicable)					X	X	X	X
Photograph(s) of wound (or closed wound area)	X	X ^c	X ^e	X ^e	X	X ^{e,f}	X ^{e,f}	X ^{e,f}
Numeric Pain Rating Scale	X ^c	X ^e	X ^e	X	X ^{e,f}	X ^{e,f}	X ^{e,f}	X ^{e,f}
VCSS	X ^c			X			X	X
EQ-5D-5L quality of life assessment		X ^c		X			X	X

^acompleted within 14 days of Screening/Baseline visit. Screening/Baseline and Enrollment/Treatment visit measurements and evaluations may occur at the same visit if patient is provided adequate time to consider and have all questions answered.

^bnot required within first week; should be scheduled per SoC for first follow-up
should be completed prior to treatment with Varithena[®]

^cadditional treatment with Varithena[®] cannot occur sooner than 5 days after index treatment
^dcollected/completed by patient using sDCT
^eInvestigator or designee to request during phone follow-up

1.2 Study objectives

The objectives of this registry are to observe the effects of Varithena® on VLU healing in patients who have the symptoms of chronic venous insufficiency, and to evaluate VLU healing rate, recurrence rate, and patient reported outcomes for Varithena® in C6 disease per Clinical Etiologic Anatomic Pathophysiologic (CEAP) classification.

1.3 Study endpoints

The primary endpoints of the study are:

- Rate of epithelial migration (mm/week) measured by wound perimeter on photograph
- Wound closure at 12 weeks (± 1 wk) post-treatment
- Time from initial treatment with Varithena® to wound closure

The secondary endpoints of the study are:

- Percent of wounds remaining closed at 3 months (± 1 wk) post-wound closure date, non-healed wounds are not included in percent calculation
- For healed wounds, rate of VLU recurrence (at same site)
- Change in pain on NPRS compared to baseline at 12 weeks (± 1 wk), 6 months (± 1 wk), 12 months (± 1 wk) post-treatment
- Change on Euroqol five dimension five level questionnaire (EQ-5D-5L) quality of life assessment compared to baseline at 12 weeks (± 1 wk) and 12 months (± 1 wk) post-treatment
- Change in Venous Clinical Severity Score (VCSS) from baseline to 12 week (± 1 wk) and 12 month (± 1 wk) follow-up
- Number of ulcer-free weeks defined as weeks from time of closure (complete epithelialization is recorded) to date of recurrence (at same site) or last contact if no recurrence (at study completion or withdrawal)

2 Changes to protocol analysis

The interim analyses were expanded to look at hospitalization and safety information. Please see section 3.8 for further details.

Additional exploratory analyses from the Wound Health Index (WHI) will not be conducted.

NPRS analyses will use data from both the sDCT and the electronic data capture (EDC). The analysis will be summarized by each week through 12 weeks, 6 months and 12 months post-treatment. Additionally, the categories by severity will not be summarized but rather the numerical scale will be summarized and presented in a shift table. Refer to section 3.5.2 for further details.

Sub-group analyses will not be performed. There is not enough data collected for the analyses to be meaningful.

3 Statistical methods and analysis

3.1 General methodology and definitions

Continuous data will be summarized with means, medians, standard deviations, quartiles (25th and 75th), minima and maxima, unless otherwise specified. Categorical data will be summarized with observed counts and percentages for each category; 95% confidence interval (CI) will be calculated using the Clopper-Pearson (1934)¹ or exact method for binary proportions. For time to event variables, the number of patients, number of events, the median and 95% CI of the median, and quartiles will be provided by the Kaplan Meier (KM) method.

Baseline is defined as the last available measurement taken before the first treatment.

Follow up wound image assessments will need to be slotted into the appropriate visit window described in the table below. Days relative to date of first treatment will be calculated as:

$$\text{Days} = \text{Date of assessment} - \text{Date of treatment} + 1$$

Visit Timepoint	Target Day	Days Relative to Date of Treatment
1 Week	7	≤ 7
2 Weeks	14	8 to ≤ 14
3 Weeks	21	15 to ≤ 21
4 Weeks	28	22 to ≤ 28
5 Weeks	35	29 to ≤ 35
6 Weeks	42	36 to ≤ 42
7 Weeks	49	43 to ≤ 49
8 Weeks	56	50 to ≤ 56
9 Weeks	63	57 to ≤ 63
10 Weeks	70	64 to ≤ 70
11 Weeks	77	71 to ≤ 77
12 Weeks	84 to 91	77 to ≤ 98
6 Month	183	153 to 213
12 Month	365	335 to 395

If any assessment has more than one wound image in the visit timepoint, the worst (largest) value will be used in the analysis. The range in the target day for weeks were used to mark all follow-up visit timepoints appropriately in instances where the sites could have used either weeks or months for the follow-up. Any assessments outside of the window will not be summarized.

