#### 7.1.1 Dosage & Administration

---

Subject is treated on Day 0 with up to 15mL of Varithena®, above and below the knee as needed, per Investigator's clinical judgement and the FPI. Each injection should not exceed 5mL. Date of treatment, number of injection sites, and volume above and below the knee is recorded in the iDCT. Appendix E: Use of Varithena® to manage patients with GSV-derived venous hypertension and chronic venous leg ulcer is provided as a guide to best practices in treating this indication.

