3.5.1.1 Rate of epithelial migration (mm/week) by perimeter

Baseline, time point value, change from baseline and percent change from baseline of the wound perimeter will be summarized by visit time points identified in section 3.1.

The wound perimeter will be evaluated for skewness using the Kolmogorov Smirnov test. In the event of significant skewness, the interquartile range will also be reported in addition to the 95% CI.

Additionally, the baseline, time point value, change from baseline and percent change from baseline will be presented for the subset of wounds that healed.

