3.5.1.2 Wound closure at 12 weeks post-treatment

The number and percentage of patients with a wound closure at 12 weeks post-treatment will be presented with a 95% CI. This will be derived as any wounds that closed on or prior to the 12 week visit in the EDC.

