3.5.1.3 Time to wound closure

Time to wound closure will be summarized by mean, median, standard deviation, quartiles, minimum and maximum. Additionally, the distribution of the time to wound closure will be analyzed by KM methodology. Any wound that was not closed will be censored at the last date on study. The 25th percentile, median and the 75th percentile will be presented along with the 95% CIs using the methodology of Brookmeyer and Crowley (1982)² using the log-log standard error. KM rates will be presented for each week with the corresponding 95% CIs using the log-log transformation methodology of Kalbfleisch and Prentice (1980)³. Plots of the KM curve will also be provided.

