3.5.2.3 Change in pain on NPRS compared to baseline

An 11-point NPRS is used to assess patient's level of pain. A patient is asked "What was your pain level at the ulcer location over the last 24 hours?" and selects a score between 0 and 10, with 0 meaning no pain and 10 meaning the worst pain.

Summary statistics for each visit time point and change from baseline for NPRS through 12 weeks, 6 months and 12 months post-treatment will be presented with 95% CI. NPRS

assessments from both the EDC and sDCT will be combined and slotted into windows found in section 3.1. If a patient has more than one assessment during a timepoint, the worst (highest) NPRS score will be used.

Additionally, NPRS assessments will be summarized using shift tables by each visit and worst value post baseline.

3.5.2.4 Change on EQ-5D-5L quality of life assessment compared to baseline at 12 weeks and 12 months post-treatment

The EQ-5D-5L is a self-administered questionnaire consisting of 5 questions pertaining to specific health dimensions (mobility, self-care, pain, usually activities and anxiety and depression), and health status rating scale (visual analogue scale [VAS]). Each dimension has 5 levels: no problems, slight problems, moderate problems, severe problems, and extreme problems. If a patient has died, the last EQ-5D-5L dimension assessment prior to death will be imputed as extreme problems (coded as 5).

The VAS records the respondent's self-rated health on a 20 cm vertical, visual analogue scale with endpoints labeled 'the best health you can imagine' (Score=100) and 'the worst health you can imagine' (Score = 0). This information can be used as a quantitative measure of health as judged by the individual respondents. If a patient has died, the last EQ-5D-5L VAS assessment prior to death will be imputed as 0.

Each one digit number expressing the level selected for each dimension can be combined into a 5-digit number describing the respondent's health state. For example, the number 11111 represents the respondent not having any problems in all five dimensions. These 5-digit numbers are health states which can be converted to an index value, where 1 represents full health and 0 is equivalent to death. A health state could be considered worse than death and the index values for those states will be less than 0. The index value will be calculated as:

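### SAP 3.1 visit windows place exact-week assessments one window late, assign Day 77 to two windows, and compare the worst of about three '12 Weeks' entries with a single baseline

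*SAP*

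**What the plan says.** SAP 3.1 slots follow-up wound images into visit windows. "Days relative to date of first treatment will be calculated as" leads into a formula that subtracts the treatment date from the assessment date and adds 1. The Protocol counts differently: "Subject is treated on Day 0" (7.1.1).

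The SAP 3.1 table sets target days 7, 14, ..., 77 for weeks 1 to 11. Each window ends on its target: '2 Weeks' is Days 8-14 and '11 Weeks' is Days 71-77. '12 Weeks' has a target of 84 to 91 and runs from Day 77 to Day 98. The reason given for that target range is that "sites could have used either weeks or months for the follow-up". '6 Month' is 153-213 around 183 and '12 Month' is 335-395 around 365.

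For several images in one window: "If any assessment has more than one wound image in the visit timepoint, the worst (largest) value will be used in the analysis". NPRS uses the same windows and a matching rule: "If a patient has more than one assessment during a timepoint, the worst (highest) NPRS score will be used" (3.5.2.3). Baseline is the single last measurement before first treatment.

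For the first primary endpoint, SAP 3.5.1.1 plans that "change from baseline and percent change from baseline of the wound perimeter will be summarized by visit time points". The other two primary endpoints do not refer to the windows. For closure at 12 weeks: "This will be derived as any wounds that closed on or prior to the 12 week visit in the EDC" (3.5.1.2). For time to closure: "Any wound that was not closed will be censored at the last date on study" (3.5.1.3).

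**The concern.** The day count and the targets follow different conventions. With treatment as Day 1, an assessment one week later is Day 8, which the table labels '2 Weeks'. Because each weekly window stops on its target, there is no room for an assessment on or just after the due date, and every misplacement in weeks 1 to 11 is toward a later label. A value labelled '2 Weeks' was then, on average, measured before two weeks, so healing looks slower than it was.

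At '12 Weeks' a second mechanism applies. The window is about three times as long as the others, and patients with open wounds go on recording weekly (Protocol 8.1.4). Taking the worst of several readings and subtracting one baseline reading pulls the change toward less improvement, even without any trend.

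These by-visit summaries are the only analysis the SAP gives for the perimeter endpoint, and NPRS change at 12 weeks is a secondary endpoint. Nothing is tested in this registry, so these descriptive values are the result that readers will use.

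**Working it through.** **Inputs.** The day formula, windows and worst-value rules come from SAP 3.1 and 3.5.2.3. Day 0 and the roughly weekly schedule come from Protocol 7.1.1 and 8.1.4. The documents give no visit-day spread, shrinkage pattern, SD or serial correlation, so those are assumptions.

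**1. The plan's own targets.** Elapsed day = SAP Day - 1. An assessment k weeks after treatment has elapsed day 7k and SAP Day 7k + 1. The stated targets 7k are reproduced on a Day 0 count and missed by one day under the SAP's formula.

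**2. Exact schedule.** In elapsed days, window k covers 7(k-1) to 7k-1 for k = 1 to 11, and '12 Weeks' covers 76 to 97.

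| Elapsed day | SAP Day | Window |
|---|---|---|
| 7 | 8 | 2 Weeks |
| 14 | 15 | 3 Weeks |
| 70 | 71 | 11 Weeks |
| 77 | 78 | 12 Weeks |
| 84 | 85 | 12 Weeks |
| 91 | 92 | 12 Weeks |
| 98 | 99 | none |

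All of weeks 1 to 11 go one window late; week 12 is right.

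**3. With spread.** Assume deviations uniform on -3 to +3 days, giving 11 × 7 = 77 cases. For k = 1 to 10, deviations -3 to -1 are correct and 0 to +3 are late. For k = 11, -3 and -2 are correct, -1 (SAP Day 77) is in two windows, and 0 to +3 are late. Correct: 10 × 3 + 2 = 32. Late: 10 × 4 + 4 = 44. In two windows: 1. Early: 0. With ±5 days (121 cases): 54 correct, 66 late, 1 in two windows, 0 early.

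**4. Entries in '12 Weeks'.** Days 77-98 are 22 days, against 7 for the other weekly windows. The endpoint's own 12 weeks ± 1 week is elapsed 77-91, or Days 78-92 on the SAP count. An exact schedule puts three weekly entries in the window (elapsed 77, 84, 91). If every visit is one day early there are four (76, 83, 90, 97). The mean under ±3 days is 22/7 = 3.14.

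**5. Perimeter, unhealed wound.** Under assumed constant shrinkage, change is proportional to elapsed time and the largest image is the earliest in the window. Understatement = 1 - (mean elapsed day used)/(target). With ±3 days and a fixed weekday for each patient:

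| Window | Mean elapsed day used | Understatement |
|---|---|---|
| 2 Weeks | 10 | 1 - 10/14 = 28.6% |
| 4 Weeks | 24 | 1 - 24/28 = 14.3% |
| 8 Weeks | 52 | 1 - 52/56 = 7.1% |
| 12 Weeks | (76+77+78+79+80+81+82)/7 = 79 | 1 - 79/84 = 6.0% |

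If deviations are independent from week to week (simulated), the figures are 33.2%, 16.6%, 8.3% and 5.1%. Measurement error is not included and would add to the '12 Weeks' figure.

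**6. NPRS at '12 Weeks'.** The expected maximum of three readings, in within-patient SDs, is the sum over the three pairs of √(2(1-ρ)), divided by 2√(2π). Independent: 3 × 1.414/5.013 = 0.85. Assumed serial correlation 0.5 (pairs 0.5, 0.5, 0.25): (1 + 1 + 1.225)/5.013 = 0.64. With an assumed SD of 1 to 2 points, that is about 0.6 to 1.7 points in unhealed patients still recording. Averaged over all patients at unhealed shares from the small foam trial in Protocol 4.1: 0.64 × 1/13 = 0.05 SD (foam arm) to 0.85 × 8/21 = 0.32 SD (compression-only arm).

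**The case against.** The strongest reply is that this is ordinary week binning. With treatment as Day 1, Days 1-7 are the first study week, 8-14 the second, and so on. SAP 3.3.1 and 3.4.1 also use '+ 1', and no slotting rule uses the target day. Eleven of eleven late needs visits exactly 7k days after treatment. One day earlier, weeks 1 to 10 are all placed correctly. The Protocol asks only for roughly weekly dressing visits, and the first follow-up is per standard of care. The overlap looks like 77 typed for 78. The worst-value rule is prespecified and conservative, and the wide 12-week target has a stated reason.

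Part of this stands. Exact-schedule placement is a limiting case, the sizes rest on assumptions, and the direction is conservative. For perimeter, three entries is toward the high end, because SAP 4.3 keeps only reviewed, evaluable images and removes those after the closure date in the EDC. Those rules also share the cause when a wound open at its week 11 photograph and closed by the Week 12 visit counts as closed but shows an open perimeter at '12 Weeks'. The unhealed shares may not transfer: this registry requires ulcers of at least 3 months and excludes wounds expected to close within 12 weeks.

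The binning reading does not rescue the table. The table states targets of 7k that its own formula misses by one, and its '6 Month' and '12 Month' windows are centred. The stated reason explains the 84-91 target only; it does not explain the overlap, the weekly windows that end on target, or worst-of-several selection.

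A reader might infer that every weekly value is a full week out, or that the closure results are biased too. The documents support neither. Early visits mostly stay in their own window, and closure at 12 weeks and time to closure do not use these windows.

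**Conclusion.** The point holds for the by-visit descriptive values of perimeter and NPRS, and only for those. The day arithmetic and the Day 77 overlap are certain. The direction is also clear: misplacement in weeks 1 to 11 is always late, and selection at '12 Weeks' favours the worse value, so both understate improvement.

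The size is conditional. Under uniform ±3 days, 44 of 77 assessments are late. Under constant shrinkage as well, perimeter change in an unhealed wound is understated by about 29-33% at '2 Weeks', falling to 5-6% at '12 Weeks'. The NPRS shift is 0.64 to 0.85 within-patient SD in unhealed patients still recording, and 0.05 to 0.32 SD over the whole group at the cited unhealed shares. It is worth correcting because rules followed as written give mislabelled weeks, and the correction is cheap.

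**What to change.** Drop the '+ 1' in the window formula only; the duration formulas in SAP 3.3.1 and 3.4.1 can stay. Then:

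- Use centred, non-overlapping windows: Week 1 = Days 1-10; Week k = 7k-3 to 7k+3 for k = 2 to 11; Week 12 = Days 81-97. If the '+ 1' is kept, the same windows are Days 2-11, 7k-2 to 7k+4, and 82-98.
- Assign the Week 12 clinic visit by its recorded visit, so a compliant visit on day 77 stays at Week 12.
- Where a window holds several values, use the Week 12 clinic value if present, otherwise the value nearest the target (84 for Week 12). Keep the worst-value rule as a sensitivity analysis.
- Treat closed wounds the same way at all visits: enter perimeter 0 at every visit from the EDC closure date until any recurrence, or at none, and label the table accordingly. Entering 0 at Week 12 only would create an artificial drop there, because SAP 4.3 removes post-closure photographs at earlier weeks.

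**Minimal change:** drop the '+ 1', start '12 Weeks' at Day 78, and end it at Day 97 so that the week 14 entry (day 98) stays out as now. The clinic visit still needs assigning by its recorded visit. This corrects exact-schedule entries and the overlap. Under ±3 days it leaves 11 × 3 = 33 of 77 late, and it does not cure the worst-value selection at Week 12.

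**Cost:** SAP wording and a small programming change, with no new data. The conservative result moves to a sensitivity table. Week 12 = 81-97 is still asymmetric around 84 and holds 17/7 = 2.43 entries on average under ±3 days, so the clinic-value rule must go with it. At ±5 days centred windows also misplace entries (22 late and 20 early of 121), but about equally in both directions.

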#### 8.1.2 Enrollment/Treatment Visit (Day 0) (Clinic)

---

Screening/Baseline and Enrollment/Treatment visit measurements and evaluations may occur at the same visit if subject is provided adequate time to consider and have all questions answered.

The following are performed at this visit:

- Collection of data prior to treatment:
  - Photograph(s) of wound in iDCT
  - VCSS
  - NPRS
  - EQ-5D-5L quality of life assessment
- Varithena® Treatment – treatment procedure and collection of treatment details

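### The Week 1 window in SAP 3.1 has no lower bound and counts the treatment date as day 1; applied literally to NPRS, it admits the pre-treatment score and rules out any Week 1 improvement

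*SAP*

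**What the plan says.** - **Day count.** SAP 3.1 defines the relative day as "Date of assessment} - \text{Date of treatment} + 1". The date of first treatment is therefore day 1.
- **Windows.** In the SAP 3.1 table the Week 1 row is ≤ 7. Every other row has a lower limit; Week 2, for example, starts at day 8.
- **Scope of the windows.** The table is introduced for images: "Follow up wound image assessments will need to be slotted into the appropriate visit window described in the table below".
- **Baseline.** "Baseline is defined as the last available measurement taken before the first treatment". The SAP does not add that this record is kept out of the windows.
- **NPRS.** SAP 3.5.2.3 says that NPRS "assessments from both the EDC and sDCT will be combined and slotted into windows found in section 3.1", and then: "If a patient has more than one assessment during a timepoint, the worst (highest) NPRS score will be used".
- **Timing of the Day 0 score.** Protocol 8.1.2 lists NPRS under "Collection of data prior to treatment". Footnote c to Protocol Table 1 also places it before treatment.
- **Timing of the first follow-up.** Protocol 8.1.3 lets the Week 1 visit fall after the first week, and trains the subject on the sDCT only at that visit.
- **Reporting.** SAP section 2 summarizes NPRS for each week through Week 12. SAP 3.5.2.3 adds shift tables by visit, and SAP 3.8 includes NPRS in the interim summaries.

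**The concern.** Three rules that are each reasonable alone combine badly: an open-ended first window, a day count that starts at 1 on the treatment date, and a worst-score rule. The limit to follow-up records is written for wound images. SAP 3.5.2.3 borrows the windows for NPRS without repeating it.

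Protocol 8.2.9 has site-assessed NPRS entered in the iDCT. If the SAP's EDC is that site-entered source, the Day 0 score is in the pool to be windowed. The cleaning steps in SAP 4.3 do not remove pre-treatment records.

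Two programmers could follow the text in good faith and produce different Week 1 results. One would allow for early pain relief. The other could show only no change or worsening, whatever the patients reported.

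**Working it through.** The plan gives no figure to reproduce here. The check runs its rules as written.

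**1. Which window does each record fall in?** Relative day = elapsed days + 1.

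| Record | Elapsed days | Relative day | SAP 3.1 window |
|---|---|---|---|
| Earliest permitted baseline evaluation (Protocol 8.2) | -14 | -13 | Week 1 |
| Day 0 score, before treatment | 0 | 1 | Week 1 |
| Follow-up 6 days after treatment | 6 | 7 | Week 1 |
| Follow-up exactly 7 days after treatment | 7 | 8 | Week 2 |

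**2. What can the Week 1 change be?** Let b be the Day 0 score, which is also baseline, and p one post-treatment score in Week 1, each from 0 to 10.

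- Literal rule: change = max(b, p) - b, which is never below 0.
- Pre-treatment record excluded: change = p - b.

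Over all 11 × 11 = 121 pairs:

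| Rule | Improve | No change | Worsen |
|---|---|---|---|
| Literal | 0 | 66 | 55 |
| Pre-treatment record excluded | 55 | 11 | 55 |

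The 66 are the 11 true ties plus the 55 improvements, which are all turned into zeros. For example, b = 6 and p = 3 gives 6 - 6 = 0 under the literal rule, against 3 - 6 = -3. These counts describe what the rule permits; they do not forecast results.

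**3. Patients without a post-treatment score by day 7.** The literal window holds only b, so the change is b - b = 0. This includes a patient whose first score comes exactly one week after treatment, because that is day 8. Excluding the pre-treatment record leaves Week 1 missing for this patient, consistent with the plan's rule of no imputation.

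**4. Illustration of size, on assumed values.** The documents give no mean, SD or Week 1 coverage for NPRS. If the true change is normal with mean μ < 0 and SD s, and every patient has a post-treatment Week 1 score, the literal mean is s·φ(|μ|/s) - |μ|·[1 - Φ(|μ|/s)].

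| μ | s | φ | 1 - Φ | Literal mean |
|---|---|---|---|---|
| -1 | 1.5 | 0.319 | 0.252 | +0.23 |
| -1 | 2 | 0.352 | 0.309 | +0.40 |
| -1 | 2.5 | 0.368 | 0.345 | +0.58 |
| -2 | 1.5 | 0.164 | 0.091 | +0.06 |
| -2 | 2 | 0.242 | 0.159 | +0.17 |
| -2 | 2.5 | 0.290 | 0.212 | +0.30 |

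If only a fraction c of patients has such a score, the rest contribute 0 and the mean is multiplied by c. With c = 0.5 and s = 2, +0.40 becomes +0.20 and +0.17 becomes about +0.08.

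A simulation that rounds scores and confines them to 0–10 (assumed baseline mean 5, SD 2.5; change SD 2; full coverage) agrees in direction: a true mean change of -0.88 reads as +0.36, and -1.73 reads as +0.15.

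**The case against.** The strongest reply is that the authors plainly meant post-treatment records. SAP 3.1 introduces the windows for follow-up assessments and defines baseline separately. A change from baseline presupposes that the baseline record is not also the follow-up value. SAP 3.5.2.3 speaks of post-treatment time points, and a sensible programmer would leave the Day 0 record out. As a statement of intent this is persuasive. It does not close the gap, because the follow-up qualifier is attached to images and nothing expressly bars the baseline NPRS from Week 1.

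The limited reach also stands as an objection. No hypotheses are tested, Week 1 is not an NPRS endpoint, and the stopping criterion in SAP 3.8 concerns hospitalizations and related serious adverse events, not pain.

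A reader might go further than the documents allow in three ways:

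- **The table of worst values after baseline.** It might seem that this table could also pick up a pre-treatment score. As worded it is limited to values after baseline, and Protocol Table 1 schedules no pre-treatment NPRS other than the Day 0 one.
- **Wound perimeter.** The largest-value rule for images ("If any assessment has more than one wound image in the visit timepoint, the worst (largest) value will be used in the analysis") might suggest the same exposure. The follow-up wording applies directly to images, so that inference is much weaker.
- **The illustrative means.** They might be read as the bias to expect. The full-coverage figures assume a post-treatment score for every patient by day 7, which a first visit at about one week makes doubtful.

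**Conclusion.** The point holds conditionally. If SAP 3.1 and 3.5.2.3 are programmed as written, the Week 1 NPRS change cannot be negative. It is exactly 0 for every patient with no post-treatment score by day 7, given the single scheduled pre-treatment score. That result is arithmetic and needs no distributional assumption. Whether the rules would be programmed that way is not settled by the SAP, and the surrounding text suggests it was not intended. The documents therefore do not support saying outright that pre-treatment pain will be counted in Week 1.

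The exposure is the descriptive Week 1 NPRS summary, the Week 1 shift table, and the interim NPRS summary if it includes Week 1. The NPRS endpoints at 12 weeks, 6 months and 12 months are unaffected, as is the table of worst values after baseline as worded. The size of any bias in the Week 1 mean rests on assumed means, SDs and coverage, so the figures above are illustrations only. The point is small in reach but should be settled before the Week 1 tables are programmed.

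**What to change.** In SAP 3.1, change the Week 1 row to days 2 to 7, or keep the row and use a pre/post-treatment flag. A lower bound of day 1 would not work, because the pre-treatment Day 0 record is itself day 1. Add one sentence: records taken before the first treatment count as baseline only and are never slotted into a post-treatment window, for NPRS as well as wound images. Refer to that sentence in SAP 3.5.2.3.

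The cost is one table row, one sentence and a cross-reference. With the day 2 bound, any score taken after injection on the treatment day is lost; the flag avoids this. Neither option moves a visit made exactly one week after treatment out of Week 2, so Week 1 may be sparse. The number of patients contributing should be shown beside each Week 1 result.

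### Taking the worst value in the 22-day Week 12 window and the 61-day 6- and 12-month windows against a single baseline value understates NPRS improvement, mainly in unhealed patients; the effect on perimeter is small at Week 12

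*SAP*

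**What the plan says.** For wound images, SAP 3.1 states: "If any assessment has more than one wound image in the visit timepoint, the worst (largest) value will be used in the analysis". For pain, SAP 3.5.2.3 pools EDC and sDCT records, slots them into the SAP 3.1 windows and adds: "If a patient has more than one assessment during a timepoint, the worst (highest) NPRS score will be used". The comparator is a single value: "Baseline is defined as the last available measurement taken before the first treatment".

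The SAP 3.1 window table gives 7-day windows for Weeks 2 to 11, days 77-98 for Week 12 (target days 84 to 91), days 153-213 for 6 months (target 183) and days 335-395 for 12 months (target 365). For the Week 12 target range the SAP offers a reason, that sites may have scheduled by weeks or by months: "The range in the target day for weeks were used to mark all follow-up visit timepoints appropriately". It offers none for choosing the maximum.

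These windows feed two endpoints. NPRS change at 12 weeks, 6 months and 12 months is a secondary endpoint, listed in SAP 1.3 with ±1 week at each time. Perimeter is the SAP's route to a primary endpoint (SAP 3.5.1.1): "change from baseline and percent change from baseline of the wound perimeter will be summarized by visit time points identified in section 3.1". SAP 3.5.2.3 also plans separate NPRS "shift tables by each visit and worst value post baseline".

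Protocol 8.1.4 has patients with open wounds photograph the wound and answer the NPRS question at weekly wound care visits until closure, including after Week 12.

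**The concern.** Baseline is one reading. The follow-up value is the highest of however many readings fall in the window. When readings vary, the highest of several is on average above a single one, so a patient whose pain has not changed appears to worsen. The more readings, the larger the shift, and their number depends on window width, on whether the wound is still open and on how faithfully the patient reports.

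The registry tests no hypothesis (SAP 1.1.1), so the estimates and their confidence intervals are the result, and an interval around a shifted mean does not reveal the shift. Week 12, 6 months and 12 months, the times named in the NPRS endpoint, would not be on the same footing as Weeks 2 to 11.

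**Working it through.** **Window widths** (last day − first day + 1), from SAP 3.1:
- Week 12: 98 − 77 + 1 = 22 days
- 6 months: 213 − 153 + 1 = 61 days
- 12 months: 395 − 335 + 1 = 61 days

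The Week 12 width is explained by its target range: 84 − 7 = 77 and 91 + 7 = 98.

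**Readings per window for an open wound**, counted over every possible starting day. The 12-month count assumes follow-up ends on days 359-373 (365 rounded to 366, ±7), because the protocol follows patients for 12 months.

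| Window | Weekly | Every two weeks |
|---|---|---|
| A 7-day window | 1 | 0-1 |
| Week 12 | 3-4 | 1-2 |
| 6 months | 8-9 | 4-5 |
| 12 months | 3-6 | 1-3 |

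SAP 4.3 removes some images, so image counts are upper limits. A healed patient normally gives one NPRS score at 6 months. A second arises if the call 3 months (91 days) after closure falls in the window, that is, closure on days 153 − 91 = 62 to 213 − 91 = 122.

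**NPRS, per patient, no true change.** Inputs are assumptions, since the documents give none: within-patient SD 0.5 to 2 points, week-to-week correlation 0 to 0.8, patient mean 3, 5 or 7, integer scores held to 0-10. The quantity is the mean of (maximum of k follow-up scores − one baseline score), over 200,000 simulated patients per setting.

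| Scores in window (k) | Shift in points |
|---|---|
| 1 | 0 |
| 2 | +0.1 to +1.1 |
| 3 | +0.2 to +1.7 |
| 4 | +0.3 to +2.0 |
| 9 | +0.5 to +2.9 |

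Nine scores means full weekly compliance, so that row is a ceiling. As an illustration with SD 1, no correlation, patient mean 5 and a true fall of 2 points: one value records −1.9 (floor effect), while the maximum records −1.1 with three scores, −1.0 with four and −0.5 with nine.

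**NPRS, shift in the endpoint mean** = unhealed share × per-patient shift, taking one score per healed patient. The shares come from studies cited in Protocol 4.1 and are assumptions for this population; exclusion 12 may select slower healers.
- Week 12: unhealed 1/13 to 8/21 in a foam sclerotherapy trial. Weekly reporting: 1/13 × 0.2 = 0.02 up to 8/21 × 2.04 = 0.78. With one score each: 0.
- 6 months: unhealed 1/13 (same trial, 24 weeks) to 34/110 (an ablation study). Two-weekly reporting at the low end: 1/13 × 0.3 = 0.02. Weekly at the high end: 34/110 × 2.94 = 0.91. Two-weekly at the high end: 34/110 × 2.30 = 0.71.
- 12 months: unhealed 12% (a perforator surgery registry). At most 0.12 × 2.51 = 0.30, and 0 with one score each.

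**Perimeter.** In a steadily shrinking open wound, the largest image in a window is the first. Shrinkage lost = days from the first image to the image nearest the target, divided by 7.
- Week 12, day 84, weekly images, seven starting days: 7, 7, 7, 0, 0, 0, 7 days; mean 28/7 = 4 days = 0.57 week. Images every two weeks: 0.
- 6 months, day 183, weekly images: 28, 28, 28, 28, 21, 28, 28 days; mean 189/7 = 27 days = 3.86 weeks. Images every two weeks: mean 3.29 weeks.

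**Two side findings.** Day 77 belongs to both the Week 11 and Week 12 windows. The 6- and 12-month windows are 183 ± 30 and 365 ± 30 days, wider than the ±1 week in SAP 1.3, and SAP section 2 does not note this.

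**The case against.** The rule is prespecified, explicit and conservative: in a single-arm, sponsor-run registry it works against the product. No test between time points is planned, and NPRS is not analysed by healing status. Patients collect records unaided, so real counts may be well below weekly, and anyone with one value in the window is unaffected. Every SD and correlation above is assumed, and the low end of the endpoint shift is negligible.

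Much of this stands as a limit on size. It does not remove the bias: a conservative rule is still a biased estimate where the estimate is the deliverable, and the amount varies with compliance and healing status.

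Three stronger readings are tempting and lack support:
- **A shift of 2 to 3 points in the reported mean.** That is the per-patient ceiling, needing eight or nine scores and high, uncorrelated variability. Patients healed by then have stopped weekly reporting.
- **A material contribution from healed patients.** The documents do not say how many wounds close on days 62-122. Healing times cited in Protocol 4.1 include a median of 54 days and means of 36 and 142 days, and pain at a closed ulcer may be low.
- **A serious distortion of the primary perimeter endpoint.** The protocol synopsis plans perimeter measurement only up to 12 weeks, where the loss is 0 to 1 week. The 3-4 week loss at 6 months applies only to wounds still open and still shrinking.

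**Conclusion.** The point holds, and the change should be made. The direction needs no assumption: a window maximum is never below the value nearest the target day, so recorded improvement is never larger and is smaller whenever that nearest value is not the highest. The effect falls mainly on NPRS in unhealed patients.

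The size is unknown. Under the assumed SDs, correlations, unhealed shares and compliance, the endpoint mean moves by near 0 to under 1 point at Week 12 and 6 months and by at most about 0.3 at 12 months. Weeks 2 to 11 are essentially unaffected. Wound closure at 12 weeks, time to closure, VCSS and EQ-5D-5L do not depend on the rule. A reader might infer that the headline healing results are compromised; they are not.

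**What to change.** In SAP 3.1 and 3.5.2.3:
- Use the assessment closest to one stated target day in each existing window: day 84 for Week 12, day 183 and day 365. Day 84 continues the 7-days-per-week targets of Weeks 1 to 11.
- Break ties in this order: on the same date, the clinic (EDC) record over the subject (sDCT) record; then the earlier date. Use the higher value only for records with the same date and source.
- Start the Week 12 window at day 78, so that day 77 belongs only to Week 11. Keep its end at day 98, so that a visit made at 3 months (about day 91) stays eligible.
- Keep the 6- and 12-month windows, because "Any assessments outside of the window will not be summarized", and state in SAP section 2 that ±30 days is wider than the ±1 week in SAP 1.3.
- Keep the worst-value rule only for the worst-post-baseline shift table, or as a sensitivity analysis.

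The cost is SAP wording and one selection rule in the program. No new data are needed and no assessment leaves the analysis windows. There are two downsides: the deliberately conservative main summary is lost, and at Week 12 a subject-entered record nearer day 84 can replace a clinic value taken near day 91.
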